# **B** Secondary Endpoints

Secondary outcome variables will be examined between the two study arms at baseline, pubertal onset and adult height (final visit). To examine sex differences, the secondary outcomes variables will be examined by-sex between the two study arms.

'Pubertal Onset' is defined as the visit when patients entered puberty (Tanner 2 breast in females, testicle size > 3mL) or completed therapy with the aromatase inhibitor and or LHRHa.

- i. Adult height achieved will also be expressed standard deviation (SD) units and in cm as the difference in height achieved in relation to their target height (i.e., mid-parental height, calculated based on their parental heights)
- ii. Height achieved (SD units) from baseline to pubertal onset
- iii. Height achieved (SD units) from pubertal onset to adult height
- iv. Predicted adult height (using Bayley-Pinneau method) at pubertal onset
- v. Predicted adult height (using Bayley-Pinneau method) change from baseline to pubertal onset
- vi. Predicted adult height (using Bayley-Pinneau method) change from pubertal onset to final height
- vii. Growth velocity (in SD units) from baseline to pubertal onset
- viii. Growth velocity (in SD units) from pubertal onset to adult height
- ix. Percent of visits with ACTH in normal range from baseline to pubertal onset
- x. Percent of visits with ACTH in normal range from pubertal onset to adult height
- xi. Percent of visits with androstenedione in normal range from baseline to pubertal onset
- xii. Percent of visits with androstenedione in normal range from pubertal onset to adult height
- xiii. Percent of visits with 17-hydroxyprogesterone in the optimal range (<1,200 ng/dL) or high (>1,200 ng/dL) from baseline to pubertal onset
- xiv. Percent of visits with 17-hydroxyprogesterone in the in the optimal range (<1,200 ng/dL) or high (>1,200 ng/dL) from pubertal onset to adult height
- xv. Percent of patients with onset of central precocious puberty (CPP)

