#### Hydrocortisone Dose Adjustment During Conventional Treatment

We will attempt to optimize the child's management during a baseline period. While administering hydrocortisone (preferably in a dose of 10-15 mg/m^2/day, and not exceeding 25 mg/m^2/day), the mineralocorticoid dose will be adjusted to maintain a normal plasma renin activity in children with 21-hydroxylase deficiency. With plasma renin activity in the normal range, hydrocortisone dose will generally be increased if:

(1) the growth rate is 2 standard deviation (SD) units or more above the median normal value for age;

(2) the rate of bone age advancement exceeds 2 years per chronologic year; or

(3) plasma 17-hydroxyprogesterone (17-OHP) levels are excessively elevated in association with growth rate and rate of bone maturation that are above the median normal values.

Because spot measurements of plasma 17-OHP correlate rather poorly with growth rate and bone maturation, plasma 17-OHP will be used as an aid to judgement rather than as a treatment goal in itself. At the present time, 0800-0900 plasma 17-OHP levels of 500 to 1300 ng/dL are considered appropriate, levels of 1300 to 3000 ng/dL prompt consideration of a hydrocortisone dose increase (assuming that plasma renin activity is normal), levels of 3000 to 6000 ng/dL prompt strong consideration, and levels >6000 ng/dL will ordinarily lead to a dosage increase.

Hydrocortisone dose will generally be decreased if:

(1) the growth rate is 2 SD units or more below the median normal value for age, if the bone age is prepubertal, or the growth rate seems inappropriately suppressed relative to age and bone age, if the bone age is in the pubertal age range;

(2) the body mass index exceeds 2 SD units above the median value for age, or if signs of Cushing's syndrome are appearing;

(3) there is no detectable bone maturation over a period of more than 6 months; or

(4) plasma 17-OHP appears excessively suppressed in association with a subnormal growth rate or rate of bone maturation. Plasma 17-OHP levels below 500 ng/dL will ordinarily raise consideration of a dosage decrease; levels below

200 ng/dL will raise strong consideration.

We have chosen a thrice-daily hydrocortisone dose schedule for this study. There are no controlled studies that compare a twice-daily and thrice-daily approach; however the thrice-daily hydrocortisone dose schedule is the most commonly used conventional regimen.

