#### Hydrocortisone Dose Adjustment During Investigational Treatment

Congenital adrenal hyperplasia occurs in several clinically distinct variants that reflect differing severity of the underlying enzymatic deficiency, even among the classic forms. For example, the salt-wasting and simple-virilizing forms of 21-hydroxylase deficiency have different clinical courses: salt-wasters experience many more episodes of adrenal crisis and may require more glucocorticoid for adequate control. Even within the salt-waster and simple-virilizer subgroups of CAH, clinical heterogeneity is seen. This may be due to varying genotypes or other unknown factors.

A hydrocortisone dose of 8 mg/m2/day was chosen in our initial pilot study based on estimates of normal production rate; however, children may vary in their glucocorticoid daily requirements. Our hypothesis that the regimen of flutamide, an aromatase inhibitor and a reduced hydrocortisone dose can normalize the growth of children with, CAH while avoiding the complications of supraphysiologic glucocorticoid, does not require identical glucocorticoid doses in all children on the new regimen. Regimens will be more closely tailored to the individual differences in glucocorticoid requirement. The hydrocortisone dose will be allowed to vary in the flutamide-aromatase inhibitor treatment arm.

With plasma renin activity in the normal range, hydrocortisone dose will generally be increased if 2 or more of the following occur:

- 1) the rate of bone age advancement exceeds 2 years per chronologic year and there is no evidence of central precocious puberty as the cause;
- 2) plasma 17-hydroxyprogesterone levels exceed 10,000 ng/dL;
- 3) plasma androstenedione levels exceed 400 ng/dL;
- 4) testosterone levels exceed 100 ng/dL in girls or prepubertal boys;

- 5) signs of virilization (clitoral growth, voice deepening, acne) on physical examination;
- 6) presence of adrenal rest tissue on testicular ultrasound in boys (see below);
- 7) evidence of macronodular disease on adrenal ultrasound or MRI (see below).

With plasma renin activity in the normal range, hydrocortisone dose may be decreased if 2 or more of the following occur:

- 1) plasma 17-hydroxyprogesterone levels are below 500 ng/dL;
- 2) plasma androstenedione levels are below 50 ng/dL;
- 3) the rate of bone age advancement is less than 1 year per chronologic year;
- 4) weight percentile is greater than or equal to height percentile.

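### Secondary endpoints xiii and xiv count every 17-OHP value below 1,200 ng/dL as optimal, with no lower limit, so they measure visits that are not high rather than visits in range

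*Combined protocol and SAP*

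**What the plan says.** The list of secondary endpoints (section B, items xiii and xiv) defines the 17-OHP measure as "Percent of visits with 17-hydroxyprogesterone in the optimal range (<1,200 ng/dL) or high (>1,200 ng/dL", once for baseline to pubertal onset and once for pubertal onset to adult height. These are the only two categories. The matching secondary objective is hormonal control, judged by the share of visits inside the normal or optimal range. The Analysis of Study section refers back to the ranges in the endpoint list and adds no low category.

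The dosing sections treat low values as a separate state.

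- **Conventional treatment** (section on hydrocortisone dose adjustment): morning "plasma 17-OHP levels of 500 to 1300 ng/dL are considered appropriate". It continues: "Plasma 17-OHP levels below 500 ng/dL will ordinarily raise consideration of a dosage decrease", and a level below "200 ng/dL will raise strong consideration".
- **Investigational treatment** (the corresponding section): "hydrocortisone dose may be decreased if 2 or more of the following occur". One of the four criteria listed is that "plasma 17-hydroxyprogesterone levels are below 500 ng/dL". This section gives no band of appropriate values.

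**The concern.** A visit with 17-OHP of 150 ng/dL scores as optimal under xiii or xiv. The same value lies outside the band that the conventional-arm dosing text calls appropriate, and is low enough for that text to raise a dose decrease strongly. The label and the dosing text therefore disagree about the same measurement.

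This matters because the trial's rationale is to control sex-steroid excess while avoiding glucocorticoid excess. An arm could show a higher percentage optimal because more of its visits are in range, because more are low, or both. The endpoint as written does not separate these, so it does not answer an objective framed as being within a range.

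**Working it through.** The plan derives no sample size or power from the 1,200 cut, so it has no figure to reproduce. The check has two parts.

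**1. The bands side by side (ng/dL)**

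| 17-OHP value | Endpoints xiii-xiv | Conventional dosing text | Investigational dosing text |
|---|---|---|---|
| below 200 | optimal | decrease strongly considered | one of four decrease criteria, two needed |
| 200 to below 500 | optimal | decrease considered | one of four decrease criteria, two needed |
| 500 to below 1,200 | optimal | appropriate | not a criterion |
| exactly 1,200 | neither category | appropriate | not a criterion |
| above 1,200 to 1300 | high | appropriate | not a criterion |

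There are three mismatches: the missing lower limit, 1,200 against 1300, and the unassigned value of exactly 1,200.

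**2. What the missing lower limit does to a comparison**

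Take 500 as the lower limit, because it is the only one in the documents that bounds a band. Then, for any distribution:

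P(500 to 1,200) = P(<1,200) − P(<500)

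so the in-range difference between arms equals the difference in percentage optimal minus the difference in percentage low. The endpoint reports the first term only.

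The documents give no 17-OHP distribution, so any size is an assumption. I assume a log-normal with median m and log-SD s between 0.5 and 1.5, so that P(<x) = Φ((ln x − ln m)/s).

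*Share of optimal visits that lie below 500*, P(<500)/P(<1,200):

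| Assumed median | Share over s = 0.5 to 1.5 |
|---|---|
| 500 | 52-69% |
| 806, the geometric midpoint √(500 × 1300) | 22-62% |
| 1300 | 6-55% |
| 3000 | 0.5-43% |

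*Two hypothetical groups*, A with median 806 and B with median 1300, at s = 1:

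- A: P(<1,200) = Φ(0.398) = 65.5%; P(<500) = Φ(−0.477) = 31.7%; in range 33.8%.
- B: P(<1,200) = Φ(−0.080) = 46.8%; P(<500) = Φ(−0.956) = 17.0%; in range 29.8%.
- A minus B: optimal 65.5 − 46.8 = 18.7 points; low 31.7 − 17.0 = 14.7; in range 18.7 − 14.7 = 4.0.

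Other settings, A minus B in points:

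| Medians A, B | s | Optimal | Low | In range |
|---|---|---|---|---|
| 806, 1300 | 0.5 | 35.1 | 14.2 | 20.9 |
| 806, 1300 | 1.0 | 18.7 | 14.7 | 4.0 |
| 806, 1300 | 1.5 | 12.6 | 11.3 | 1.3 |
| 806, 3000 | 0.5 | 75.4 | 17.0 | 58.4 |
| 806, 3000 | 1.0 | 47.5 | 28.0 | 19.5 |
| 806, 3000 | 1.5 | 33.4 | 25.9 | 7.5 |

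For 806 against 1300 the low part peaks at 16.1 points, near s = 0.7. The labels A and B stand for no particular arm, and exchanging them reverses every sign.

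*1,200 against 1300*: the largest possible P(1,200 to 1300) over all medians is 6.4% at s = 0.5, 3.2% at s = 1.0 and 2.1% at s = 1.5. This mismatch is small beside the missing lower limit.

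**The case against.** The strongest defence is that the definition is open. Both cut-points are printed, so anyone can see that percentage optimal means percentage below 1,200. The list uses *normal* for ACTH and androstenedione and *optimal* only for 17-OHP, which is compatible with a deliberate one-sided measure of insufficient suppression. That stands: the cut is usable if read as *not high*. It does not rescue the label, because the objective is about being within a range and the only two-sided 17-OHP band in the protocol is narrower on the low side.

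The bands elsewhere are titration guides rather than outcome definitions. The conventional-arm section plays down single values: "Because spot measurements of plasma 17-OHP correlate rather poorly with growth rate and bone maturation", the measurement serves as an aid to judgement. This also stands, and it limits the point.

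A reader might infer two stronger things that the documents do not support.

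- **That a low value shows over-treatment.** The conventional-arm decrease criterion on 17-OHP requires apparent suppression together with subnormal growth or bone maturation, and the investigational rule needs two criteria. A low visit is flagged, not diagnosed.
- **That the endpoint is biased towards a known arm.** In the conventional arm an increase is considered from 1300, while in the investigational arm 17-OHP counts towards one only above 10,000. That suggests more low visits under conventional treatment. But the conventional increase criterion on 17-OHP also requires growth and bone maturation above the median, the same section prompts decreases below 500, and no data by arm are given. For xiv the contrast weakens further, since after age 14 boys in both arms receive conventional treatment and after 13 girls receive it plus flutamide. Direction is unknown, and nothing shows that the apparent benefit of the investigational regimen would be inflated.

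Finally, glucocorticoid excess is partly captured by hydrocortisone dose (xviii), cumulative exposure (xix), bone maturation (xvi), BMI, and years of unchanged bone age (xvii). The last is close to the conventional decrease criterion that "there is no detectable bone maturation over a period of more than 6 months". These limit what is lost, but they do not make the 17-OHP percentage interpretable as in-range control.

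**Conclusion.** Wrong as written, and minor. The stated rule conflicts with the protocol's own 17-OHP bands, and following it counts possibly over-suppressed visits as success on an in-range objective. The identity in the check holds for any distribution. Every size above rests on assumed log-normal distributions and shows what could happen, not what will. The consequence is confined to the 17-OHP part of one secondary objective; adult height and the sample size are untouched. One condition remains: SAP Appendix A, to which the Analysis of Study section refers, was not in the text available for this review. If it already defines a low category, only the wording conflict is left.

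**What to change.** Check SAP Appendix A first. Then:

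1. Reconcile the 17-OHP bands across the secondary endpoint list and the two hydrocortisone dose-adjustment sections: the lower limit, 1,200 against 1300, and the value of exactly 1,200. The sponsor chooses the limits and states whether one set applies to both arms.
2. Keep the below-1,200 measure, but name it *not high* instead of *optimal*.
3. Report beside it, descriptively, the percentage of visits low, in range and high, by arm and for each of the two periods.
4. Because the trial is open-label, fix the limits before any comparison of 17-OHP by arm, or label the split post hoc.

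The cost is a wording change and one table built by recoding values already collected. The downside is one more category to report.

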## **C. Exploratory Endpoints**

i. Insulin resistance based on HOMA-IR-at the final visit

- ii. BMI (as SD units) change from baseline to 'pubertal onset' visit
- iii. BMI (as SD units) change from 'pubertal onset' to adult height
- iv. BMI (as SD units) at adult height

- v. BMD (Z-score) at adult height
- vi. Age at menarche

vii. Percent of patients (females only) with normal menstrual cyclicity at adult height

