# Précis

To test the hypothesis that the regimen of flutamide (an antiandrogen), testolactone or letrozole (an inhibitor of androgen-to-estrogen conversion), and reduced hydrocortisone dose can normalize the growth and adult stature of children with congenital adrenal hyperplasia, and can avoid the complications of supraphysiologic glucocorticoid dosage, 60 children with this disorder will be randomized to receive either the above regimen or conventional treatment until they have reached age 13 years in a girl or age 14 in a boy. After these ages boys will receive conventional treatment and girls will receive conventional treatment plus flutamide. In girls, flutamide will be continued until 6 months after menarche. All children will be followed until they have attained final adult height. The principal outcome measures will be adult height, body mass index, and bone density.

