### Secondary Objectives

- To assess the safety and tolerability of antiandrogen, aromatase inhibitor and reduced hydrocortisone dose combination therapy.
- To assess the effect of antiandrogen, aromatase inhibitor and reduced hydrocortisone dose combination therapy on height gain, growth velocity and bone maturation prior to puberty.
- To assess the effect of antiandrogen, aromatase inhibitor and reduced hydrocortisone dose combination therapy on height gain and bone maturation during puberty
- To assess the effect of antiandrogen, aromatase inhibitor and reduced hydrocortisone dose combination therapy on development of TART in males and establishment of menstrual regularity in females
- To assess the effect of antiandrogen, aromatase inhibitor and reduced hydrocortisone dose combination therapy on fasting glucose, body mass index, and bone mineral density
- To assess hormonal control based on percent of visits within the normal (or optimal) range for 17OHP, androstenedione, PRA and ACTH
- To assess sex differences in outcomes.

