Choice of medication will be based on patient and family preferences. Families will be counseled on the advantages and disadvantages of these two therapies. Both medications are known to effectively suppress the hypothalamic-pituitary-gonadal axis. Known side effects include rash, and local injection site reactions (milder with Deslorelin). Lupron has the advantage of monthly administration and the disadvantage of an increase risk of local injection site abscess formation (Deslorelin may cause redness at the injection site but has not been reported to result in abscess formation). Lupron also may require more dose adjustments in the beginning of therapy. Anaphylactoid reactions are an extremely rare risk for both medications. Children will return to the NIH day hospital 3 months after starting LHRH analog therapy for evaluation of hypothalamic-pituitary-gonadal suppression. Those patients who are currently being treated with Deslorelin (previously under protocol 79-CH-112) will be continued on Deslorelin or switched to Lupron, depending on patient preference.

Once degree of CAH control has been judged optimal, children will be randomized to receive either the regimen of flutamide, testolactone or letrozole, and reduced hydrocortisone dose or conventional treatment (with hydrocortisone and fludrocortisone) until the age of 13 in the girls and 14 in the boys. At that time the regimen of flutamide, testolactone, and reduced hydrocortisone dose will be discontinued in boys so that the subjects can progress through puberty. At age 13 years, girls who are receiving flutamide and testolactone or letrozole therapy will discontinue the aromatase inhibitor therapy (to allow normal progression of puberty) and continue flutamide (to continue androgen blockade). Flutamide therapy will continue until 2 years after menarche or when final height is reached, whichever occurs first.

Children who are also receiving concurrent LHRH analog to suppress central puberty will also discontinue this agent at age 13 in the girls or age 14 in the boys. The operational definition of age 13 or 14 will be the NIH study visit that is closest to their thirteenth or fourteenth birthday. The operational definition of attainment of final height, as in our other long-term trials, will be the study visit at which the incremental growth over the previous 12 months declines to less than 1.5 cm (0.6 inch).

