(6) A leuprolide stimulation test, to assess pubertal status of the hypothalamic-pituitarygonadal axis will be performed at the first visit and all subsequent visits after the child has reached a bone age of 10 in boys or 9 in girls, or if there is clinical suspicion of hypothalamic-pituitarygonadal activation (i.e. testicular enlargement in boys, breast tissue in girls). Children who are started on an LHRH analog for central precocious puberty and those who switch LHRH analog medication type will have leuprolide stimulation test performed 3 months after beginning treatment to confirm efficacy of this treatment. Additional leuprolide stimulation testing while receiving an LHRH analog will only be done if clinically indicated. This testing will resume once the patient is taken off LHRH analog therapy. Measurement of gonadotropins by third-generation immunochemiluminometric assays (ICMA) will be done. Blood withdrawal: 12 mL.

(7) Measurement of plasma 17-hydroxyprogesterone, DHEA-S, androstenedione, estradiol, testosterone, cortisol, and ACTH, estradiol starting as near 0800 h as feasible. The morning hydrocortisone dose will be held until after these samples have been obtained. Blood withdrawal: 18 mL.

(8) Blood to be frozen for possible future hormone measurements: 17 mL.

(9) Upright and supine plasma renin activity. Blood withdrawal: 14 mL.

(10) Routine CBC, thyroid panel and SMAC. Blood withdrawal: 8 mL.

(11) One-hour cortrosyn (ACTH) test to assess levels of steroid intermediates in response to ACTH stimulation. Cortisol, 17-hydroxyprogesterone, androstenedione, and DHEA will be measured at time 0 and 60 minutes after ACTH bolus infusion. Blood withdrawal: 24 mL. This test will be performed at the beginning and end of the study, and, if indicated, at some other visits.

(12) Fasting glucose, insulin and leptin levels. Blood withdrawal: 5 mL.

(13) Lipid profile. Blood withdrawal: 2.5 mL.

(14) Plasma and urinary catecholamines and metanephrines Blood withdrawal: 20 mL.

(15) Bone densitometry (DEXA): to be performed at start of treatment, annually thereafter (e.g., every other NIH visit), and at attainment of final adult height, to measure bone density of the forearm, femoral neck, and spine (AP and lateral).

(16) MRI abdomen: to be performed after 2-3 years on the protocol and after the patient's 6th birthday.

(17) Boys will have a testicular ultrasound and girls will have a pelvic ultrasound done

each visit.

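### Bone density and glucose/insulin endpoints are listed only at adult height or the final visit, after the planned end of the regimen, so two of the three components of one secondary objective have no listed on-regimen comparison

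*Combined protocol and SAP*

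**What the plan says.** The Précis sets out to test whether the regimen "can avoid the complications of supraphysiologic glucocorticoid dosage", and counts bone density among the principal outcomes. Secondary Objectives turns this into an assessment of the effect of "combination therapy on fasting glucose, body mass index, and bone mineral density".

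The matching endpoints are in section C, Exploratory Endpoints. Bone density appears once, as "BMD (Z-score) at adult height". Glucose metabolism appears once, as "Insulin resistance based on HOMA-IR-at the final visit". BMI has three entries, one of which covers the treatment period: "BMI (as SD units) change from baseline to 'pubertal onset' visit".

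On treatment, the Précis says: "After these ages boys will receive conventional treatment and girls will receive conventional treatment plus flutamide". The ages are 13 for girls and 14 for boys. The Protocol section adds that at that point "the regimen of flutamide, testolactone, and reduced hydrocortisone dose will be discontinued in boys so that the subjects can progress through puberty". For girls the same section stops the aromatase inhibitor at 13 and continues flutamide. It does not mention their hydrocortisone; the return to conventional treatment comes from the Précis.

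On data collection, item 15 of the Protocol evaluations has DEXA "to be performed at start of treatment, annually thereafter", and again at final height. Fasting glucose and insulin (item 12) are among the evaluations made at 6-month visits.

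**The concern.** The hypothesis is about what a lower hydrocortisone exposure, combined with androgen blockade and estrogen suppression, does to children while they receive it. For bone and glucose metabolism, the listed endpoints look only after the main treatment contrast is planned to have ended.

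This matters in both directions. A metabolic or bone benefit that fades on return to conventional dosing would be reported as no difference. A bone deficit that arises during years of aromatase inhibition and later recovers would appear in no listed endpoint. The second is a safety question for a regimen that lowers estrogen, and section D, Safety Endpoints, names no bone measure.

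**Working it through.** **1. The plan's own figure.** The only sample-size calculation, in Analysis of Study, is for height: SD 6 cm, 80% power, p<0.05, with a two-tailed test. The normal approximation n = 2 × (1.96 + 0.84)² × (SD/difference)² gives 23 per group for 5 cm and 16 for 6 cm. The exact two-sample t-test gives 23.6, rounded up to 24, and 16.7, rounded up to 17. These match the stated 24 and 17. No variance, difference or power is given for bone density, glucose or HOMA-IR.

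**2. Endpoint timing against scheduled data.**

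| Measure | Listed reading in the treatment period | Listed reading at adult height or final visit | Scheduled during the regimen |
|---|---|---|---|
| BMI | Change, baseline to pubertal onset | Yes | Height and weight, 6-monthly |
| Bone density | None | Yes | DEXA at start and annually |
| Fasting glucose | None | None of its own | 6-monthly |
| HOMA-IR | None | Yes | Fasting glucose and insulin, 6-monthly |

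The gap does not reflect the plan's general approach. Testicular adrenal rest tumours are read at pubertal onset and adult height, and hydrocortisone dose is summarised by period.

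**3. Treatment status at the listed reading.** In boys all three components have stopped. In girls the aromatase inhibitor has stopped and, according to the Précis, so has reduced hydrocortisone. Whether girls are still on flutamide is unclear. The Précis ends it 6 months after menarche; the Protocol section ends it 2 years after menarche, or at final height if that comes first. Under either rule a girl may be off flutamide when she is measured.

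**4. How much data goes unused.** Assume a boy randomised at age 6. He has 14 − 6 = 8 years of planned regimen, hence about 8 annual scans and 8 × 2 = 16 fasting samples after baseline. No listed bone or glucose endpoint uses them.

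**5. What fading would do (illustration only).** Assume a bone density Z-score SD of 1, which the documents do not give. The difference detectable with 80% power is 0.83 at 24 per arm and 0.74 at 30 per arm. Suppose an on-regimen difference of that size has partly faded by adult height. At 24 per arm:

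- 75% retained: 0.62, power about 56%
- 50% retained: 0.41, power about 29%
- 25% retained: 0.21, power about 11%

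The percentages are the same at 30 per arm. The retained fractions are an assumed range, and the documents do not say whether any fading occurs.

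**6. Which earlier visit to use.** Section B, Secondary Endpoints, lets the pubertal-onset visit be set by entry into puberty or by completing the aromatase inhibitor or LHRH analog. Only one arm receives the aromatase inhibitor, so the visit can be triggered differently in the two arms. The Protocol section defines the age-13/14 visit as the NIH visit nearest the birthday, for all children. That definition does not depend on arm.

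**The case against.** The strongest reply is that reading these outcomes at adult height is a legitimate choice. The Précis makes adult height, BMI and bone density the principal outcomes and follows every child to adult height. A comparison by randomised arm at that point is valid and answers a question that families care about. This stands: the comparison is not an error, only an answer to a different question.

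A reader might infer that the whole objective on glucocorticoid complications is tested off the regimen. The documents do not support that. BMI change to pubertal onset covers the treatment period, and the protocol itself gives obesity as an example of harm from glucocorticoid excess. Hydrocortisone dose by period and cumulative glucocorticoid exposure are also endpoints, although they measure exposure and not complications.

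The analysis section may also intend more for bone density than section C lists. It calls bone density a secondary outcome and refers to the final value, yet places it in a list to be modelled at baseline, pubertal onset and final visit. Section B applies the same three time points to secondary variables. One reading therefore gives bone density a pubertal-onset comparison. It conflicts with section C and does nothing for glucose or insulin, which the analysis section omits. SAP Appendix A might settle the matter but was not available.

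Nor should a reader infer that bone safety goes unwatched. DEXA is annual, and a data safety monitoring committee evaluates the study data each year. What is missing is a listed comparison between arms.

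**Conclusion.** The point holds in limited form. As section C is written, bone density and fasting glucose/insulin, two of the three components of a stated secondary objective, have no listed comparison during the regimen, and fasting glucose has no endpoint of its own. The adult-height readings can show a lasting effect but not an on-regimen effect, whether benefit or harm. The primary endpoint is untouched.

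A reader might go further and conclude that a real effect will be diluted by some stated amount. No such amount can be derived from the documents; the power figures above rest on an assumed SD and assumed retention.

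The conclusion rests on the planned sequence, in which the regimen stops before adult height is reached, and on Appendix A not already listing on-regimen readings.

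**What to change.** In section C and in Analysis of Study, add comparisons by randomised arm of:

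- bone density Z-score, from the last DEXA at or before the age-13/14 visit;
- fasting glucose at that visit;
- HOMA-IR at that visit.

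Give each as the value and as the change from baseline. A pubertal-onset reading may be shown alongside for consistency with BMI. Keep the adult-height readings and label them post-regimen, lasting-effect outcomes. List on-regimen bone density change in section D, Safety Endpoints.

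Two points of wording also need attention. Bone density is principal in the Précis, secondary in Secondary Objectives and Analysis of Study, and exploratory in section C; give it one status, and state in Analysis of Study at which time points it is modelled. The flutamide stopping rules for girls in the Précis and the Protocol section contradict each other and must be reconciled, because they determine what treatment the adult-height reading reflects. If Appendix A already covers any of this, align the protocol text with it.

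The cost is changed wording and a few more secondary or exploratory comparisons. No new procedure is needed. Because DEXA is annual, the chosen scan may precede the visit by up to about a year.
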